6.1.2 Participant exclusion criteria

Lacking capacity to provide fully informed written consent: The capacity to consent to
participate in the study will be assessed and recorded using a Mental Capacity ACT (2005)
assessment tool developed by Norfolk and Suffolk NHS Foundation Trust. Participants will not be
included in the study if they are unable to provide this.

- Currently receiving ongoing formal psychological therapy: Participants will be asked to report any ongoing treatment they are receiving from healthcare services during the screening session.
 Participants currently receiving formal psychological therapy such as CBT, psychodynamic psychotherapy, systemic therapy and counselling will be excluded.
- Experiencing disabling medical or mental health problems making participation inappropriate or impractical: Participants will be asked to report any ongoing untreated condition during the screening session. Following the baseline assessment, the participant's GP will be informed of their involvement in the study, and any concerns raised by their GP regarding their involvement will be followed by a full discussion with the participant.
- Expressing active suicidal intent: The risk of suicide will be assessed during the screening session. This will be assessed using the suicide risk assessment protocol co-developed with Norfolk and Suffolk NHS Foundation Trust. This protocol has been used across multiple studies run by our team. Those presenting suicidal ideation with active intent will be excluded.

Potential participants with insufficient understanding of English to complete screening measures and engage in the intervention will be encouraged to bring a family member or a friend who can support the participant and act as an interpreter. This approach was recommended by PPI members from ethnic minority groups. If this option is not available, a professional interpreter can be arranged through the third company, which UEA already has a contract in place. If the study team needs to directly contact another family member or an interpreter regarding the participant such as arranging the appointment, verbal consent will be obtained from the participant for doing so.

6.2 Recruitment and participant flow

Patient recruitment and flow, starting from referral, screening, through follow up and inclusion in primary analysis, will be illustrated through a diagram as indicated in the Appendix, consistent with the CONSORT guidelines. Detailed summaries of reasons for non-attendance to screening and ineligibility will be presented in tables alongside the flow diagram. Additionally, the number of participants referred, screened and randomised by recruitment resources (i.e. NHS sites, Participant Identification Centres and other community resources such as local carer groups and Join Dementia Research) will also be reported.

6.3 Withdrawal

Withdrawal from the study between follow-up visits will be summarised with tables showing detailed reasons (if provided). Non-adherence to treatment does not constitute study withdrawal.

6.4 Baseline participant characteristics

A comparison will be made of baseline characteristics between the treatment groups. This will be through the use of summary statistics alone with no inferential analyses. The summaries of continuous variables will include the number of observations used, along with the mean, median, standard deviation, inter-quartile range, minimum, and maximum values, as deemed suitable for the

distributional form of the data. Categorical variable summaries will consist of the number of observations used, as well as the count and percentage of observations within each category.

We will focus our reporting and analysis on the overall scores obtained from each questionnaire. Subscales or domains will only be reported and analysed if specifically indicated otherwise.

The following participant variables will be reported at baseline (except for STTS-R which will only be collected at 12 weeks post-randomisation):

- (i) Demographic details, including age, gender and ethnicity
- (ii) Total GAD-7 score and GAD-7 severity range
- (iii) PHQ-9
- (iv) CompACT
- (v) EACQ
- (vi) STTS-R (treatment arm only)
- (vii) EQ-5D-5L
- (viii) ICECAP-O
- (ix) Modification CSRI
- (x) Expectations about treatment
- (xi) Treatment preference

6.5 Treatment summary and compliance

The intervention involves participants completing a maximum of eight online sessions along with two one-to-one sessions via telephone or video call within a 12-week period. Participants who complete six or more online sessions will be considered treatment completers.

We will provide the following compliance summaries:

- Number and percentage of participants who attended various number of online sessions, categorised from 0 to 8 sessions.
- Mean (and SD), median, minimum, and maximum online sessions attended.
- Number and percentage of participants attending one or two one-to-one sessions, or none at all.
- A table detailing reasons for withdrawal from the intervention.
- Adherence rate, calculated by dividing the number of completers by the total number of participants allocated to the intervention group, regardless of the number of sessions completed.

7. Analysis

7.1 Outcome definitions

7.1.1 Primary outcome

The primary outcome is anxiety symptoms as assessed by the Generalized Anxiety Disorder-7 (GAD-7 [16]) at 12 weeks. In addition to the Mean (and SD), the proportions of participants falling into different severity ranges (mild, moderate, severe) at each time point will be reported.

7.1.2 Secondary outcomes

Clinical outcomes

- Patient Health Questionnaire-9 (PHQ-9 [18]): A 9-item self-report questionnaire assessing the severity of depressive symptoms. Both GAD-7 and PHQ-9 are used routinely in NHS psychological services for assessing recovery.
- Comprehensive Assessment of Acceptance and Commitment Therapy processes (CompACT [19]): A 23-item self-report questionnaire assessing psychological flexibility, which is commonly used in ACT studies. The total score and three subscale scores (Openness to Experience, Behavioural Awareness and Valued Action) will be used.
- Experiential Avoidance in Caregiving Questionnaire (EACQ [20]): A 15-item self-report questionnaire assessing experiential avoidance (one component of psychological flexibility) in the caregiving context. The total score and three subscale scores (Active Avoidant Behaviours, Intolerance of Negative Thoughts and Emotions Towards the Relative and valued action and Apprehension Concerning Negative Internal Experiences Related to Caregiving) will be used.
- Satisfaction With Therapy and Therapist Scale-Revised (STTS-R [21]): A 12-item self-report questionnaire assessing satisfaction with therapy and satisfaction with the therapist. The subscale scores (Satisfaction with therapy subscale, Satisfaction with the therapist and Outcome/Global improvement) will be used.

Cost-effectiveness measures (mainly to be used for a health economic analysis)

- EQ-5D-5L [22]): A 5-item self-report questionnaire assessing health-related quality of life.
- ICEpop Capability measure for Older people (ICECAP-O [23]): A 5-item questionnaire assessing capabilities that are required to have a high quality of life in older adults.
- Modified Client Service Receipt Inventory (modified CSRI [24]): An interview-based measure of health and social care service utilisation. This scale will be used to monitor TAU received in both arms during the trial and to calculate patient costs.

Potential Sources of bias

Expectations about treatment and participants' intervention arm preference are potential sources of bias that can affect treatment outcomes. These measures will be collected during the baseline session prior to randomisation, after participants are given a rationale for iACT4CARERS.

- Expectations about treatment: Two questions asking how much participants expect their symptoms and life to improve if they receive iACT4CARERS will be used (collected on a five-point Likert scale from 0 to 4).
- Treatment preference: Two questions asking how much they hope to receive iACT4CARERS and TAU alone without iACT4CARERS will be used (collected on a five-point Likert scale from 0 to 4).

Intervention fidelity measures

- ACT Fidelity Measure (ACT-FM [25]): All written feedback provided online by therapists will be recorded and randomly selected scripts will be reviewed and rated by independent ACT experts using an adapted form of the ACT-FM to check for intervention fidelity.
- Therapist response time: The time gap between the participant leaving a comment and their therapist providing a response will be collected for each session. Therapists are directed to provide feedback within three working days, where possible, but no later than five working days (i.e., before the next session is made available).

The scoring for each outcome measure is summarised in Table 1.

Outcome variable	Version number (if applicable)	Calculation required	Reference
GAD-7		 Sum all 7 items to calculate the total score (ranges between 0 and 21). Determine severity categories using the following cut-offs: Minimal (0-4), mild (5-9), 10-14 (moderate) and severe (15-21). The total score and severity category for each participant are automatically recorded in REDCap. However, if one or more items are missing, these fields will be left blank. 	[16]
PHQ-9		 Sum all 9 items to calculate the total score (ranges between 0 and 27). The total score for each participant is recorded in REDCap. However, if one or more items are missing, this filed will be left blank. 	[18]
CompACT		 Sum responses for each of the three subscales (Openness to Experience; Behavioural Awareness; Valued Action) and the scale as a whole (CompACT Total score). Twelve items are reverse scored before summation (items 2, 3, 4, 6, 8, 9, 11, 12, 15, 16, 18, and 19). 	[19]
		Openness to Experience (ranges between 0 and 60)	

Table 1 Outcome measure scoring

	 Calculated as the sum of scores for items: 2 (reversed), 4(reversed), 6(reversed), 8(reversed), 11(reversed), 13, 15(reversed), 18(reversed), 20, and 22. 	
	 Behavioural Awareness (ranges between 0 and 30) Calculated as the sum of scores for items: 3(reversed), 9(reversed), 12(reversed), 16(reversed), and 19(reversed). 	
	 Valued Action (ranges between 0 and 48) Calculated as the sum of scores for items: 1, 5, 7, 10, 14, 17, 21, and 23. 	
	 CompACT Total (ranges between 0 and 138) Calculated as the sum of the three subscale scores. 	
	 The subscale and total scores are recorded in REDCap. However, if one or more items are missing, these fields will be left blank. 	
EACQ	 Sum responses for each of the three subscales (Active Avoidant Behaviours; Intolerance of Negative Thoughts and Emotions Towards the Relative; Apprehension Concerning Negative Internal Experiences Related to Caregiving) and the scale as a whole (EACQ Total score). Two items are reverse scored before summation (items 6 and 8). 	[20]
	 Active Avoidant Behaviours (ranges between 6 and 30) Calculated as the sum of scores for items: 3, 7, 10, 11, 12, and 15. 	
	 Intolerance of Negative Thoughts and Emotions Towards the Relative (ranges between 4 and 20) Calculated as the sum of scores for items: 1, 4, 2, and 5. 	
	 Apprehension Concerning Negative Internal Experiences Related to Caregiving (ranges between 5 and 25) Calculated as the sum of scores for items: 6(reversed), 9, 8(reversed), 13, and 14. 	
	 EACQ Total (ranges between 15 and 75) Calculated as the sum of the three subscale scores. 	

	• The subscale and total scores are recorded in REDCap.
	However, if one or more items are missing, these fields will be
	left blank.
STTS-R	• Sum responses for each of the three subscales except for the [21] Outcome subscale (Satisfaction with therapy; Satisfaction with the therapist; Outcome).
	Satisfaction with therapy (ranges between 6 and 30)
	 Sum the scores of all even number items.
	• Sum the scoles of an even number items.
	Satisfaction with the therapist (ranges between (ranges between 6 and 30)
	 Sum the scores of all odd number items excluding item 13.
	Outcome/Global improvement (ranges 1 and 5)
	 The score of item 13 alone.
	• The subscale scores are recorded in REDCap. However, if one
	or more items are missing, these fields will be left blank.
EQ-5D-5L	• The scores need to be calculated manually, outside REDCap [22] for this scale.
	EQ-5D-5L descriptive system
	 This scale will be mainly used for the health economic
	analysis. For descriptive statistics, sum scores for each
	statement for total score (ranges between 5 to 25). Each
	statement is scored according to levels of perceived problems,
	coded as: I have no problems = 1; I have slight problems = 2, I
	have moderate problems = 3, I have severe problems = 4, I am unable to = 5.
	 Report frequency of each level reported (e.g., X% reported
	Level 1), or dichotomise the levels into 'no problems' (i.e. level
	1) and 'problems' (i.e., levels 2 to 5) and reporting frequency
	of reported problems (source:
	https://www.unmc.edu/centric/_documents/EQ-5D-5L.pdf).
	EQ-5D-5L visual analogue scale
	 Report number entered by participant on scale of 0-100. Bresent both a measure of the control tondency and a
	Present both a measure of the central tendency and a
	measure of dispersion (mean and SD, or if skewed, median and 25th, 75th percentiles; source:
	https://www.unmc.edu/centric/_documents/EQ-5D-5L.pdf).
	https://www.unne.cuu/centre/_uocunents/cq-50-5c.purj.

ICECAP-O	• The scores need to be calculated manually, outside REDCap for this scale.	[23]
	 This scale will be mainly used for the health economic analysis. For descriptive statistics, sum scores for each statement for total score (ranges between 5 to 25). Each statement is scored according to levels of perceived capability, coded as: I am able to do all of the things = 4; I am able to do many of the things = 3; I am able to do a few of the things = 2; I am unable to do any of the things = 1. Report frequency of each level reported (e.g., X% reported Level 4). 	
Modification CSRI	 This scale will be mainly used for the health economic analysis. For descriptive statistics, report frequency of each response (e.g., X% providing up to 1 hours per week, X% 1-2 hours) or the central tendency and a measure of dispersion (e.g., support from other family carers in hours per week) depending on the nature of questions. 	[24]
Expectations about treatment	 The score needs to be calculated manually, outside REDCap for this scale. Sum responses for two five-point Likert scales (0 to 4). The total score ranges between 0 and 8. 	NA
Treatment preference	 The score needs to be calculated manually, outside REDCap for this scale. The second item is reverse scored before summation (#106 in REDCap). Sum responses for two five-point Likert scales (0 to 4). The total score ranges between 0 and 8. 	NA

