6.10.4.5 Missing Data

Participants will be unable to submit any questionnaire with any missing fields when an online version of CRFs is used. Therefore, there will be no missing data from questionnaires completed online. This will be clearly explained in the information sheet. There may be some missing data when
participants choose to use paper CRFs. Also, some missing data may result from loss to follow-up. A small percentage (5% or less) of missing data is generally inconsequential[45] in which case we will carry out analysis of available data without imputation. If more than 5% of data is missing, we will adopt appropriate technique for handling missing data depending on the mechanism of missingness. Specifically, if the mechanism of missing data is found to be missing at random (MAR), i.e., missingness is predicted by observed covariates, we will employ multiple imputation to handle missing data[46], where the imputation model will include observed predictors of missing data. The estimates obtained from the analysis of imputed datasets will be combined using Rubin's rule[47].

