7.3 Sensitivity analyses

7.3.1 Sensitivity to missing data

Participants will be unable to submit any questionnaire with any missing fields when an online version of case report forms (CRFs) are used. Therefore, there will be no missing data from questionnaires completed online. This will be clearly explained in the information sheet. There may be some missing data when participants choose to use paper CRFs. Also, some missing data may result from loss to follow-up. A small percentage (5% or less) of missing data is generally inconsequential in which case we will carry out analysis of available data without imputation. For both the primary and secondary outcomes the extent and possible patterns of missing data will be checked. The relationship between baseline variables and missing primary outcome data will be examined. Additional data analysis will be undertaken in the event of missing data in the primary outcome and/or baseline covariates being more than 5%. A sensitivity analysis using multiple imputation will be considered to minimise potential bias affecting estimated treatment effect. Factors to include in the imputation model will be those that are likely to be related to the outcomes and those related to missingness. The imputation model will include the variables of the analytical model [26,27].

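### One missing item blanks the whole score under SAP Table 1, and no rule scores a part-answered paper form; the cost is small for GAD-7 and larger for CompACT and EACQ

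*SAP*

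**What the plan says.** SAP section 7.1.2, Table 1, sets out the scoring of each questionnaire. For GAD-7 it gives "Sum all 7 items to calculate the total score (ranges between 0 and 21"), adds that REDCap records the total and severity category, and continues: "However, if one or more items are missing, these fields will be left blank". PHQ-9 and STTS-R carry the same condition. For CompACT and EACQ it covers subscales and total in one sentence: "The subscale and total scores are recorded in REDCap. However, if one or more items are missing, these fields will be left blank".

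SAP 7.3.1 says where gaps can arise. Online: "Participants will be unable to submit any questionnaire with any missing fields when an online version of case report forms (CRFs) are used". On paper: "There may be some missing data when participants choose to use paper CRFs". Protocol 6.10.4.5 says the same. If 5% or less of the data are missing, "we will carry out analysis of available data without imputation". Above 5%, the SAP will consider multiple imputation as a sensitivity analysis. Protocol 6.10.4.5 commits to it above 5% when data are missing at random, and does not call it a sensitivity analysis.

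SAP 7.2 takes the 12-week GAD-7 as the outcome of the primary model. Neither document contains a prorating rule, a minimum number of answered items or item-level imputation.

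**The concern.** The only stated rule for a part-answered form is that its score is absent. Three consequences follow if the plan is applied as written.

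- A carer who returns a 12-week GAD-7 with 6 of 7 answers contributes no outcome to the primary model, although the true total is known to within 3 points of 21.
- CompACT and EACQ have subscales built from separate items. Read literally, one gap in one subscale empties the others too.
- Online forms cannot be submitted with gaps, so the loss falls only on paper users and grows with scale length. GAD-7, PHQ-9, EACQ and CompACT would then be analysed on somewhat different sets of carers for a purely procedural reason.

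At stake is some precision, mainly on the mechanism measures, and a small further departure of the analysed sample from the randomised one. If the statistician instead scores such forms by hand, the rule is chosen after data are in view, which defeats the purpose of a prospective SAP (SAP section 3).

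**Working it through.** **The plan's own figure.** SAP 4.3 uses d = 0.35, two-sided 5% and 90% power. The normal approximation, 2 × (1.960 + 1.282)² / 0.35² = 171.5, rounds up to 172 per arm. The two-sample t calculation gives 172.5, so 173, as stated. Allowing for 30% dropout, 173 / 0.7 = 247.1, so 248 per arm and 496 in total. The plan's figures reproduce. The expected number at 12 weeks is 496 × 0.7 = 347.2 (173.6 per arm), with power Φ(0.35 × √(173.6/2) − 1.96) = 90.3%.

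**Structure of the scales (Table 1).** GAD-7 has 7 items scored 0-3 and PHQ-9 has 9. CompACT is described thus: "A 23-item self-report questionnaire assessing psychological flexibility". Its subscales list 10, 5 and 8 items; together these are items 1 to 23, each once. EACQ lists 6 + 4 + 5 = 15 items. The item lists and ranges are consistent, so the only fault is the missing-item rule.

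**Assumptions.** The documents give neither the share of paper forms nor the item non-response rate q. I take 5-30% paper and q from 0.5% to 3%, independent across items.

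**Share of paper forms blanked**, 1 − (1 − q)^k for k items:

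| q | GAD-7 (7) | PHQ-9 (9) | EACQ (15) | CompACT (23) |
|---|---|---|---|---|
| 0.5% | 3.4% | 4.4% | 7.2% | 10.9% |
| 1% | 6.8% | 8.6% | 14.0% | 20.6% |
| 2% | 13.2% | 16.6% | 26.1% | 37.2% |
| 3% | 19.2% | 24.0% | 36.7% | 50.4% |

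**Scores lost at one visit** = 347.2 × paper share × share blanked. Power is the formula above with the reduced n:

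| Paper, q | GAD-7 lost | Power, primary | Recovered by a one-missing-item rule | CompACT lost |
|---|---|---|---|---|
| 5%, 0.5% | 0.6 | 90.3% | 0.6 | 1.9 |
| 10%, 1% | 2.4 | 90.1% | 2.3 | 7.2 |
| 20%, 2% | 9.2 | 89.6% | 8.6 | 25.8 |
| 30%, 3% | 20.0 | 88.6% | 18.2 | 52.5 |

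The recovered column uses the probability of exactly one gap, 7q(1 − q)^6. For example, at 10% paper and q = 1%: 347.2 × 0.10 × 7 × 0.01 × 0.99^6 = 2.3.

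**What the literal subscale reading costs.** At q = 1%, 20.6% of paper CompACT forms lose all four scores. Scored from its own items, Openness would be lost on 1 − 0.99^10 = 9.6% of forms, Behavioural Awareness on 1 − 0.99^5 = 4.9% and Valued Action on 1 − 0.99^8 = 7.7%. For EACQ, 14.0% compares with 5.9%, 3.9% and 4.9% for its 6-, 4- and 5-item subscales.

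**Accuracy of prorating.** I simulated a one-factor 7-item scale scored 0-3 (200,000 records, latent inter-item correlation 0.4-0.6). A score prorated from 6 items correlated 0.98-0.99 with the full score, with a root mean square error of about 0.7-0.9 points on a scale with SD about 4.4-5.5.

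**The case against.** **The sentence describes database fields, not an analysis exclusion.** Other rows of Table 1 say that a score is calculated outside REDCap, so these notes may only tell the statistician where each score comes from. That is fair. But no other scoring is given for a part-answered form, so the plan as written supplies no value.

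**A reader might infer that one missing CompACT item certainly blanks every subscale.** The text does not settle this. Each subscale is defined as the sum of its own items, so the condition could apply only to the fields affected. The literal reading is broader, and the SAP should say which is meant.

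**A reader might infer that imputation offers no remedy.** That goes too far. With 27% lost in the feasibility study and 30% dropout assumed (SAP 4.3), the 5% trigger will almost certainly be met. SAP 7.3.1 admits predictors related to the outcome, and nothing excludes the answered items. What stands is that the answered items are not named, and that the SAP places imputation outside the primary analysis.

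**Gaps may be repaired before scoring.** Central staff review forms for missing key data (Protocol 6.11.4.2), the database supports queries (6.10.2), and postal follow-up includes a support call (6.6.1.2, follow-ups). These can reduce gaps, but no step for obtaining an unanswered item is stated. Baseline GAD-7 is largely protected, because eligibility and minimisation need it.

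**The assumptions may be generous.** Online entry is preferred and internet access is required for entry, so 30% paper looks high. If blanks cluster, as with a skipped page, fewer forms are affected and prorating rescues fewer of them.

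**Complete-item scoring is a defensible pre-specified choice.** It is, and whether each instrument's source permits prorating cannot be checked from these documents. It still discards answers already collected when a cheap alternative exists.

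**Conclusion.** The concern holds as a cheap improvement that should be made, not as a threat to the trial. Table 1 states a blank-if-any-item-missing rule for five questionnaires, both documents expect gaps on paper, and nothing scores a part-answered form.

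For the primary outcome the effect is small: about 2 of 347 scores at an assumed 10% paper and 1% per item, and 20 scores with a fall of under 2 percentage points in power at the assumed extreme. These power figures use the plan's unadjusted two-sample calculation. The effect is larger for CompACT and EACQ, where the literal rule also removes complete subscales. All sizes rest on assumed paper and non-response rates and on independent gaps.

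A reader might also infer bias between arms. The documents do not support that: carers state their follow-up mode at screening and baseline, before randomisation (Protocol 6.6.1.1), and STTS-R is collected in the treatment arm only.

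**What to change.** Amend Table 1 before any analysis.

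1. State that each subscale is scored from its own items, whether or not items of other subscales are missing. This has no downside.
2. For multi-item scales, after reverse-scoring, take the mean of the answered items times the number of items when no more than 20% are missing; otherwise the score is missing. This allows one gap in GAD-7 (1/7 = 14%) and one in PHQ-9 (1/9 = 11%). The 20% limit is a proposal and should be checked against each instrument's scoring source.
3. Compute CompACT and EACQ totals from their own items. Table 1 now defines them as sums of subscales, which may be missing.
4. Score the 4-item EACQ subscale (one gap is 25%) and the single-item STTS-R outcome only if complete.
5. State a rounding rule for GAD-7 severity bands. Six answers summing to 8 prorate to 8 × 7/6 = 9.33, which falls between mild (5-9) and moderate (10-14).
6. Derive scores in the analysis code from the stored items, and name the answered items as predictors in the imputation model. Report part-completed forms by arm, and repeat the primary analysis with fully answered forms only.

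The cost is SAP wording and a few lines of code, since paper responses are already entered by hand. The downside is small measurement error in a few prorated scores, which the fully-answered repeat would expose.
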